the Mount Sinai Medical Center, St Luke's and Roosevelt Hospital sites of HIV care which currently provide care to 9,031 HIV-positive patients. Based on quality improvement statistics from these sites, 45% of the patients are age 50 or older, 94% of patients are on ART, 73% of these patients have an HIV viral load less than 48 copies/mL, and 75% of these patients have a nadir CD4 count of below 250 cells/mm³. Applying these percentages to the 9,031 patients, 2,091 meet the primary eligibility criteria. Taking into account additional inclusion/exclusion criteria, it is estimated that 1,800 patients would meet eligibility criteria and it is therefore only necessary to recruit less than 7% of the eligible patients to recruit the 120 subjects. Based on the demographics from subjects recruited in previous studies and number of patients at each site, it is expected that the recruited sample will be approximately 76% male, 40% black, 36% Hispanic, 19% non-Hispanic white, and 1% Asian. In order to ensure recruitment of adequate numbers of blacks, Hispanics, non-Hispanic whites and women, the PIs will continually monitor the demographics of recruited subjects and stop recruitment of blacks or Hispanics if either group reaches 45% or 40% respectively of the planned sample, stop recruitment of whites if it reaches 25% of the planned sample, and stop recruitment of males if it reaches 80% of the planned sample. To minimize attrition, incentive payments for study visits will be gradually increased over time.

Inclusion criteria: 1) HIV-infected for 5 or more years; 2) On ART for 5 or more years; 3) HIV viral load consistently <48 copies/mL for the last year; 4) no anticipated changes in ART by provider or patient; 5) CD4 nadir of 250 cells/mm³ or less; 5) Fluency in the English language; 6) Age 50 years or older; 7) Willingness to complete the entire MBSR or HEP interventions; 8) baseline IL-6 level of 1.17 pg/mL or greater. Exclusion criteria: 1) Having participated in an MBSR course in the past; 2) Current meditation and/or yoga practice; 3) Began psychiatric medications in the past 2 months or plans to discontinue psychiatric medications; 4) Currently receiving statins, steroids, or immunosuppressant drugs; 5) Women who are pregnant or plan to become pregnant in the next year.

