The list of eligible patients identified through the electronic medical record will be reviewed with each HIV Primary Care Provider (PCP) and permission requested from them for the RC to contact each of their eligible patients at the next clinic visit. If a PCP indicates not to contact a patient, the reason will be recorded. The patient's participation in this study will play no role in how the PCP manages his or her care. If permission is given, the RC will use a scripted explanation to explain the study to the patient including the inclusion and exclusion criteria. If the patient is interested in participating, he or she will undergo informed consent. The RC will place emphasis on the time demands of the intervention in order to screen out those that are unlikely to adhere to the demands of the intervention. After obtaining Informed Consent, the RC will assign a study identification number, collect demographic and contact information, and a blood sample will be collected to determine baseline IL-6 levels. Each consented subject that meets all inclusion criteria will be invited to join the study and complete three subsequent research visits (separate from the MBSR or HEP sessions). At these visits, the psychological assessments will be completed and blood will be collected. Separate blood draws will also occur within one week of each of these 3 study visits for the second measure of IL-6 values.

Measurement of Biological Markers: Inflammatory biomarkers to be measured belong to one or more of four broad-spectrum categories: i) general (IL-6, CRP), ii) innate immunity (IL-6, CRP, sCD14), iii) microbial translocation (sCD14), and, iv) system wide-associated (CRP, d-dimer). The selection of biological markers for the study is based on three primary considerations: i) markers which have been unequivocally demonstrated to be increased in HIV-infected adults when compared to uninfected counterparts, ii) markers with strong translational medicine correlates connecting basic immunological inflammation with clinical outcomes, and, iii) markers demonstrating scientific reliability with respect to laboratory assay measurements.^{15-17,22,60,61}

The four markers selected using these criteria are:

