Potential Challenges, Proactive Measures, Alternative Strategies The key challenges when measuring the proposed 4 biological markers (IL-6, hsCRP, sCD14 and d-dimer) result from: 1) expertise and quality control of assay execution, 2) diurnal rhythm expression, and, 3) within subject variability.⁸⁸ To account for these potential challenges proactive measures have been established. First, and critically important, has been the establishment of collaboration with Drs. [name] and [name]. The level of expertise, experience and quality control provided by this lab assures reliability on recorded data. All frozen samples will be processed for execution of biological assays at a single run after completion of all collections. This measure controls for any potential variability during assay execution. The potential challenge of diurnal rhythm expression for all of the 4 biological markers will be addressed by strict serum collection in the three hour period between 3 pm and 6 pm. All blood samples for the entirety of the study will be collected in this three-hour time period and processed immediately, followed by immediate storage at a minus 80-degree freezer, assuring preservation of each marker. The concern of within subject variability is a key issue for IL-6 in particular.⁸⁹ For that reason, a critical approach measure has been established: two separate collections of blood for IL-6 measure at each time point, averaging the value for the two. Although it is recognized that this poses an additional level of demand on subjects, as they have to report to the study site twice for each of the three study time points, given the crucial role of IL-6 as the key biological marker, collecting two separate measures at each study time point provides the strongest level of reliability.

Measures of Psychosocial Stress and Mindfulness: Psychosocial measures will be assessed at 3 time points: baseline, after the 8 week course, and after the subsequent 6 month booster sessions.

The Patient Reported Outcomes Measurement Information System (PROMIS) is a system of highly reliable self-report measures, with substantial qualitative and quantitative evidence supporting validity, developed with funding from NIH.^{90,91} Two instruments have been selected from the PROMIS Neuro-QOL Item Bank v1.0 Short Forms: Anxiety and Fatigue (8 validated items each, for a combined instrument of 16 items).

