Aim 1: To assess the effect of MBSR on biomarkers of chronic inflammation in HIV-infected adults with well-controlled plasma viremia. The primary outcome for the analyses of treatment effectiveness will be IL-6 levels. We will use mixed linear models to assess the effect of the intervention on markers of inflammation. The model will include fixed effect terms for treatment group, time, and time-treatment interactions. In secondary analyses, we will similarly assess the effect of the intervention on secondary markers of inflammation (CRP, sCD14, d-dimer) using appropriate adjustments for multiple comparisons. If there are imbalances in patients’ characteristics across groups, statistical adjustment including these factors as covariates will be performed. All analysis will use an intent-to-treat principle. **Power Calculation:** Sample size calculations were based on the following assumptions: 1) mean baseline IL-6 of 2.0 pg/ml (SD:0.5)^{17,98}; 2) stable IL-6 levels in the control arm; 3) clinical significant effect of MBSR will be a net reduction of IL-6 of >0.5 pg/ml.^{98,99} Under these assumptions, a sample size of 100 patients (50 per group) will provide a power >80% using 2-sided test and a 0.05 significance level. One hundred and twenty study participants will be enrolled. Dropout rates reported in the literature for MBSR studies range significantly (range 0 to 48%, mean 10%). In order to lean on a conservative side a higher dropout rate of 15% is estimated for this study. With a 120 enrolled, a 15% dropout rate provides 102 completed participants. It is quite feasible to recruit 120 patients from this estimated eligible sample of 1,800 subjects at the three recruitment sites (requiring participation of ~7% of the eligible sample).

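### The pre-randomization screening IL-6 value has no role in the primary analysis; using it beside the baseline average would be a cheap, modest gain in precision

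*Combined protocol and SAP*

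**What the plan says.** All references are to section C, Approach, of the combined document.

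- **Participants and Recruitment:** once consent is given, "a blood sample will be collected to determine baseline IL-6 levels". Those who meet all criteria are then invited to three later research visits.
- **Inclusion criteria:** entry requires a "baseline IL-6 level of 1.17 pg/mL or greater".
- **Intervention, challenges paragraph:** the baseline evaluation takes place on a different date from consent.
- **Measurement of Biological Markers:** blood is taken once at screening and twice within a week at each of three time points, seven draws in all. For the endpoint, the challenges paragraph specifies "two separate collections of blood for IL-6 measure at each time point, averaging the value for the two". It gives variation within subjects as the reason for the second draw.
- **Aim 1:** "The model will include fixed effect terms for treatment group, time, and time-treatment interactions". Covariates come in only if patient characteristics turn out imbalanced.

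No passage gives the screening value a use after entry.

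**The concern.** The plan asks each subject to attend twice per time point in order to reduce noise in IL-6. Two draws in the same week share that week's state, for example a passing cold, so averaging them cannot remove it. The screening draw comes from another occasion and therefore carries information on the subject's usual level that the baseline average lacks. It is measured before treatment, already paid for, and complete by design. Leaving it out makes the interval for the MBSR effect somewhat wider than the collected data allow. It also leaves out a useful predictor for subjects who miss a baseline or follow-up draw.

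**Working it through.** **1. The plan's own power figure.** Aim 1 gives 50 per group, SD 0.5 and a "net reduction of IL-6 of >0.5 pg/ml", and says this "will provide a power >80% using 2-sided test and a 0.05 significance level". The standard error is 0.5 × √(2/50) = 0.10, and 0.5/0.10 = 5, so power is Φ(5 − 1.96) = 99.9%. The statement is true with a wide margin. For a change score with zero correlation, the SD is 0.5 × √2 = 0.707, the standard error 0.141 and power 94.2%.

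**2. Variance model (assumed).** Set the variance of one draw to 1 = p + w + d: stable person share p, week-level share w, draw-level share d. Let S be the screening draw, B the two-draw baseline mean and Y a two-draw follow-up mean. Then var(S) = 1, var(B) = var(Y) = p + w + d/2, and every covariance between occasions is p.

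**3. Worked example: p = 0.5, w = 0.25, d = 0.25.** Here var(B) = var(Y) = 0.875.

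- Change Y − B: 2 × (0.875 − 0.5) = 0.750.
- Entry cut: (1.17 − 2.0)/0.5 = −1.66 SD, which removes about 5% and multiplies var(S) by 0.813. So var(B), var(Y) and cov(Y,B) each fall by 0.25 × 0.187 = 0.047, to 0.828, 0.828 and 0.453.
- Adjusting for B only: 0.828 − 0.453²/0.828 = 0.580.
- Adjusting for B and S: explained variance is 0.25 × (1 + 0.875 − 2 × 0.5)/(0.875 − 0.25) = 0.350, leaving 0.875 − 0.350 = 0.525. Selection on S does not alter this, because S is conditioned on.
- Further cut from S: 1 − 0.525/0.580 = 9.5%. With 102 completers, 102/0.905 ≈ 113, about 11 more.

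**4. Range with the same entry cut, w from 0.15 to 0.25.**

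| Stable share p | Further cut from S |
|---|---|
| 0.2 | 3% |
| 0.3 | 5% |
| 0.4 | 7% |
| 0.5 | 9% to 10% |
| 0.6 | 12% |
| 0.7 | 14% to 15% |

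If half of those screened were excluded, the cut would be 4% to 10% for p of 0.4 to 0.7.

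**5. Drift of the stable level.** Assume two months from screening to baseline and a stable-component correlation of 0.95 per month, with the example's shares and no entry cut. At 8 weeks (two months), cov(B,S) = cov(Y,B) = 0.5 × 0.95² = 0.451 and cov(Y,S) = 0.5 × 0.95⁴ = 0.407. The residual variance goes from 0.642 to 0.603, a cut of 6.2% in place of 10.9%. Eight months after baseline the cut is 2.9%. At 0.90 per month the two cuts are 3.5% and 0.8%. With p = 0.7, w = 0.25 and the entry cut, 0.95 per month gives 6.9% at 8 weeks. The range is therefore about 1% to 7%.

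**6. Which models gain (constant stable level).** S is uncorrelated with Y − B, since 0.5 − 0.5 = 0.

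- S added as a main effect to the group, time and interaction model: standard error 0.0978 with and without S in a simulated trial.
- S as an extra occasion with a common mean while baseline means stay arm-specific: variance remains 0.750.
- Screening and baseline means both common to the arms: 0.525, the same as adjusting for both.

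**The case against.** The strongest reply is that nothing in the plan's own figures calls for more precision. That stands: power is about 99.9% on the stated inputs. Even if power were exactly 80%, the example's gain would raise it only to Φ(2.80/√0.905 − 1.96), about 84%.

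Using a screening measurement only for eligibility is also a legitimate choice, and most of the improvement comes from conditioning on baseline. Both stand. The screening value is an addition to that step, not a substitute for it.

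Some stronger readings are tempting but not supported:

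- **That the value is discarded.** The plan is silent. The imbalance clause could admit it conditionally, and the variables for imputation are left open. Randomization after screening is likewise implied by the order of steps, not stated.
- **That the trial is underpowered or its comparison invalid.** The calculation in step 1 contradicts the first, and nothing here biases the arm comparison.
- **That a cut of more than 20% is available while keeping a change contrast.** In the example a fall from 0.750 to 0.580 (23%) needs the screening value weighted into the baseline. That is inadvisable, because the value is selected at 1.17 pg/mL or above. It may also come from another assay run: the biomarker section puts all frozen samples in one run at the end, yet entry needs a result earlier.

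**Conclusion.** The point holds as a low-cost efficiency improvement. Each enrolled subject should have a pre-randomization IL-6 value to which the primary analysis assigns no role. Used correctly, it lowers residual variance beyond baseline adjustment by about 3% to 15% for a stable share of 0.2 to 0.7, or about 1% to 7% with drift. These figures depend on assumed reliability, an assumed gap from screening to baseline, and a screening draw as precise as the others; the documents settle none of these. The gain matters mainly if the effect is small, which the plan itself calls plausible against the active control, or if IL-6 varies more than the SD of 0.5 suggests. Selection at entry applies equally to both arms and does not bias the comparison.

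**What to change.** In Aim 1, model post-baseline IL-6 on arm, visit, arm-by-visit, the two-draw baseline average and the screening value, with each covariate interacted with visit and on the same scale as the outcome. An equivalent is a longitudinal model in which the screening and baseline means are both constrained to be common to the arms. Keep the screening value as its own term and do not average it into baseline. Include it in any imputation model. State when randomization occurs relative to screening, and reconcile the single end-of-study assay run with the need for a screening result at entry.

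The cost is a reworded primary model, which is more than one added term because the stated model does not condition on baseline, and a few degrees of freedom. No new sample, visit or patient is needed. It should be fixed before any outcome data are seen by arm.

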(3) Soluble CD14 (sCD14): Evidence suggests that damage to the gastrointestinal immune system, and the consequential microbial translocation, are key elements in immune activation during chronic HIV infection. CD14+ macrophages secrete sCD14, which interacts with bacterial products from microbial translocation, such as lipopolysaccharides. sCD14 has been demonstrated to be at higher levels in HIV-infected individuals compared to uninfected counterparts.^{17,19} Several studies of HIV-infected individuals have identified sCD14 as a biological marker linked to impaired cognitive function, increased risk of age-associated end-organ diseases, and mortality.^{20,21,25,76-78} In more recent findings, sCD14 as a marker of gut epithelial barrier dysfunction (along with IL-6, CRP and D-dimer) was found to be a predictor of mortality in treated HIV infection.⁶⁶

(4) D-dimer: D-dimer is a protein fragment produced from fibrin degradation, used as a marker of a hypercoagulable state and of endogenous fibrinolysis.⁷⁹ Recent studies have identified D-dimer not only as a predictor of cardiovascular disease,^{79,80} but also of mortality in HIV-infected individuals.^{17,22,23,60} The role of D-dimer as a strong translational medicine predictor in HIV infection has recently been confirmed.^{65,66,68,74,81,82}

The appropriateness of the biological markers selected for this study is not only evident from the significant number of clinical studies cited above, but also by numerous abstracts of preliminary studies presented at the 2015 Conference on Retroviruses and Opportunistic Infections investigating these molecules.⁸³⁻⁸⁷

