Subjects will go to the Mount Sinai Clinical Research Unit (CRU) at screening time (after signing consent) plus two separate times within one week at each of the 3 study time points (baseline, after 8 week course, after 6 month booster sessions). Blood for serum analysis will be drawn into 4ml vacutainers and processed within 6 hrs. Tubes will be centrifuged and nonhemolyzed serum aliquoted and stored frozen at -80°C until analysis. Assays for the four selected biological markers will be conducted at the Icahn School of Medicine at Mount Sinai in the laboratory of immunologist Dr. [name]. The core facility supervised by Dr. [name] incorporates years of extensive experience in laboratory expertise with a wide variety of immunological approaches. Analysis of high sensitivity CRP, sCD14 and IL-6 will be performed using Quantikine ELISA kit (BIO RAD) and BioTek programmable plate reader and d-dimer will be analyzed using EMD Millipore bead based ELISA kit and a Luminex 200.

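### D-dimer is to be assayed in serum, the only specimen collected; in-tube clotting is a possible, avoidable source of measurement error in this secondary endpoint

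*Combined protocol and SAP*

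**What the plan says.** All references are to section C (Approach) of the combined protocol and SAP.

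- **Specimen.** The collection paragraph under Measurement of Biological Markers says: "Blood for serum analysis will be drawn into 4ml vacutainers and processed within 6 hrs". It continues: "Tubes will be centrifuged and nonhemolyzed serum aliquoted and stored frozen at -80°C until analysis". The assays for the four markers follow directly, with no second specimen type.
- **Scope.** The Potential Challenges paragraph after it confirms that serum serves every marker: "diurnal rhythm expression for all of the 4 biological markers will be addressed by strict serum collection in the three hour period".
- **What d-dimer is for.** Item (4) of the marker list says: "D-dimer is a protein fragment produced from fibrin degradation, used as a marker of a hypercoagulable state and of endogenous fibrinolysis".
- **Assay.** "d-dimer will be analyzed using EMD Millipore bead based ELISA kit and a Luminex 200". The specimen types for which that kit is validated are not stated.
- **Time to processing.** The collection paragraph allows up to 6 hours. The Potential Challenges paragraph says samples "will be collected in this three-hour time period and processed immediately, followed by immediate storage at a minus 80-degree freezer".
- **Role in the analysis.** Aim 1 places d-dimer among the "secondary markers of inflammation (CRP, sCD14, d-dimer) using appropriate adjustments for multiple comparisons". Aim 2 correlates the psychosocial scores with IL-6 and the other inflammatory markers.

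**The concern.** Serum is obtained by letting blood clot, and clotting lays down fibrin. D-dimer is a fragment of fibrin, chosen here to reflect clotting and fibrinolysis in the patient. Measuring it in a clotted tube lets handling act on the same pathway, possibly to a degree that depends on how long the blood sits before it is spun. IL-6, CRP and sCD14 are not clot products, so the point is confined to d-dimer.

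If handling does add error, the d-dimer treatment comparison loses precision and its correlations with the stress scores in Aim 2 are pulled towards zero. Timing matters too: all samples are held frozen for a single assay run after collection ends. A specimen problem found at that stage could not be repaired, because no plasma would have been stored.

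**Working it through.** **1. Is serum really the only specimen?** The collection paragraph describes a single stream: draw for serum, spin, aliquot serum, freeze. The Potential Challenges paragraph ties serum collection to all four markers. No citrate, EDTA or other plasma tube appears anywhere; the word plasma is used only for viremia. So the plan states a specimen choice and does not merely leave it open.

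**2. Do the plan's safeguards reach this error?** The plan lists three measurement challenges: assay quality, diurnal rhythm and within-subject variability. Specimen type is not among them.

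| Safeguard | What it controls | Controls clotting in the tube? |
|---|---|---|
| Single assay run | Run-to-run assay variation | No |
| Draws between 3 pm and 6 pm | Diurnal rhythm | No |
| Two draws averaged per time point | Within-subject variation, for IL-6 only | No; d-dimer is not averaged |
| Immediate processing | Time on the clot | In part, but contradicted by the 6-hour allowance |

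Because the two processing statements differ, time to spin could vary from sample to sample. Any effect would then not have to be a constant shift that cancels in within-patient change.

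**3. How large might it be?** The documents give no d-dimer variance, target effect or assay error, so there is no plan figure to reproduce. The only stated power calculation concerns IL-6. What follows is a hypothetical scale.

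Inputs:
- Completers: 120 × 0.85 = 102, or 51 per arm (Aim 1, power calculation).
- Two-sided alpha of 0.05, before any multiplicity adjustment.
- Assumed standardised effect d = 0.56, picked only because it gives 80% power with 51 per arm.
- Assumed added error variance k, as a fraction of the original variance.

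Formulas:
- Power comes from the noncentral t distribution with 100 degrees of freedom and noncentrality 0.56 × √(51/2) / √(1+k) = 2.828 / √(1+k).
- The interval widens by √(1+k) − 1.
- A correlation shrinks by the factor 1/√(1+k).

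| k | Noncentrality | Power | Interval wider by | Correlation multiplied by |
|---|---|---|---|---|
| 0 | 2.828 | 80.0% | 0% | 1.00 |
| 0.10 | 2.696 | 76.1% | 4.9% | 0.95 |
| 0.25 | 2.529 | 70.7% | 11.8% | 0.89 |
| 0.50 | 2.309 | 62.8% | 22.5% | 0.82 |
| 1.00 | 2.000 | 50.8% | 41.4% | 0.71 |

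Nothing in the documents says which row applies, and the first row is not excluded.

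**The case against.** The strongest reply is that the plan defines d-dimer as a product of fibrin breakdown, whereas clotting in a tube is fibrin formation. To get from one to the other, one must suppose that fibrin in the tube is also broken down, or traps fragments, by an amount that varies between samples. The documents do not say so. Nor do they say which specimens the kit is validated for; documented validation in serum would remove most of the point. The power table would look the same for a noise complaint about any marker, and it uses a simple two-sample comparison where the plan specifies a mixed linear model. One laboratory, one collection unit, one tube size, concurrent arms and the statement on immediate processing all limit variation in handling.

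Much of this stands. The size of the error is unknown, and the table is illustrative. What survives is narrower: the plan commits to a clotted specimen for a fibrin-derived marker, gives no evidence that the specimen suits the kit, and contradicts itself on how long the blood may wait.

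A reader might also infer that the d-dimer values cannot be set against the prognostic studies the plan cites for choosing the marker. The documents do not say which specimen those studies used, so that inference is not supported.

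**Conclusion.** The point holds as a possible, avoidable source of measurement error in one of three secondary inflammation markers. It rests on two things: the plan's serum-only collection, and the general fact that serum is the fluid left after clotting, read alongside the plan's own definition of d-dimer. The size of the error cannot be determined from the documents and may be small.

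Three stronger readings are tempting and should be resisted:

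- **That the d-dimer data would be unusable.** The documents give no error size and no validated specimen type, so they cannot show this.
- **That the treatment comparison would be biased.** Both arms share the same tubes, laboratory and assay run and are conducted concurrently. The expected consequence is lost precision.
- **That the trial's main conclusion is at risk.** The primary endpoint is IL-6, which is not a clot product and is not affected by this argument.

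This is a low-cost improvement worth making before the first draw, because it cannot be made once all samples have been collected.

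**What to change.** In the collection paragraph under Measurement of Biological Markers:

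1. Add one small anticoagulated plasma tube to an existing draw at baseline, after the 8-week course and after the 6-month booster period. Use an anticoagulant for which the d-dimer kit is validated, and assay d-dimer from that plasma.
2. Keep serum for IL-6, hsCRP and sCD14, and state the specimen type for each marker.
3. Reconcile the 6-hour allowance with the statement on immediate processing, so that one uniform time to spin applies to every sample.

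**Cost.** At most about 120 × 3 = 360 extra tubes and their aliquots, slightly more blood per draw, and a short edit to the laboratory manual and the consent form. No extra visit or needle stick is needed, because the draws are already scheduled.

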General Study Design: The proposed study is a prospective, randomized, clinical trial with attention control under the direction of the dual PIs, a behavioral scientist and a virologist. The study team is also made up of investigators from infectious diseases, mind-body medicine, geriatrics, and biostatistics. Subjects will be randomized to participation in an 8-week group MBSR course as the study intervention or to the Health Enhancement Program (HEP) as the active control arm. The study population will consist of 120 individuals, 50 years old or older, long-term (5 years on ART or longer) HIV-infected adults with well-controlled plasma viremia. Randomization will be stratified to achieve balanced distribution between the groups based on gender and study site. The experimental group will participate in the 8-week MBSR course followed by six, once-per-month booster sessions, and the control group will participate in HEP, a validated group attention control condition for MBSR maintaining subjects inert to mindfulness, with additional monthly educational meetings for

six months. Both groups will be evaluated using two sets of measures: biological markers associated with chronic inflammation (IL-6, CRP, sCD14, d-dimer) and measures of psychosocial stress (anxiety, depression, fatigue, and mindfulness). Subjects will be assessed at three time points: baseline, 8 weeks (immediately after completion of MBSR intervention), and 6-months post MBSR course (immediately after completion of booster sessions). We will use mixed linear and structural equation model to test study hypotheses.

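### A single assay run does not remove plate-to-plate error in about 720 IL-6 samples; the plan has no plate allocation rule or plate term, so that error may enter the change in the primary outcome

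*Combined protocol and SAP*

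**What the plan says.** All references are to the combined protocol and SAP, section C, Approach.

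- **Size and schedule** (General Study Design): "The study population will consist of 120 individuals, 50 years old or older", and "Subjects will be assessed at three time points: baseline, 8 weeks", with a third assessment six months after the course.
- **IL-6 draws** (Measurement of Biological Markers, paragraph on potential challenges): "two separate collections of blood for IL-6 measure at each time point, averaging the value for the two".
- **Assay** (Measurement of Biological Markers): IL-6, CRP and sCD14 use "Quantikine ELISA kit (BIO RAD) and BioTek programmable plate reader"; d-dimer uses a bead-based kit.
- **Assay timing** (same challenges paragraph): "All frozen samples will be processed for execution of biological assays at a single run after completion of all collections". The next sentence is the claim at issue: "This measure controls for any potential variability during assay execution".
- **Primary analysis** (Aim 1): a mixed linear model for IL-6 with fixed effects for group, time and their interaction. No plate or batch term is listed.
- **Sample handling**: the assay description has blood "processed within 6 hrs", while the challenges paragraph has it "processed immediately, followed by immediate storage at a minus 80-degree freezer" and relies on this to preserve the markers.

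The documents give no plate format, no number of replicate wells, no rule for placing samples on plates and no statement that the laboratory is blind to arm.

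**The concern.** The plan itself lists assay execution and its quality control as a key challenge, and gives the single run as the answer. For a plate-based assay that answer is incomplete. Samples run in the same week on different plates still carry different plate shifts.

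The primary question is whether IL-6 changes differently in the two arms. If a participant's visits sit on different plates, the difference between two plate shifts is added to that participant's change. At best this is noise that could have been avoided. If plates happened to follow arm, a plate shift could not be told apart from a treatment effect, and a larger sample of participants would not cure it unless it also meant more plates. All outcome samples are held until the end, so the layout is entirely in the trial's hands, but the plan does not use that freedom.

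**Working it through.** **Inputs from the documents.** 120 enrolled; 3 visits; 2 IL-6 draws per visit; 15% dropout leaving 102; mean IL-6 2.0 pg/ml, SD 0.5; target net reduction 0.5 pg/ml; 50 per group; two-sided 0.05; stated power above 80%.

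**Assumptions, not in the documents.** 96-well plates with 16 wells for standards, leaving 80 single-well or 40 duplicate samples; between-plate CV 5%, 10% or 15%; within-person correlation 0.5, with 0 as a check.

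**1. The plan's power.** SE = 0.5 × √(2/50) = 0.10. Then 0.5/0.10 = 5, and power = Φ(5 − 1.96) = 99.9%. This satisfies the stated bound with much room.

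**2. Samples.** 120 × 3 × 2 = 720. If all dropouts leave after baseline: 120 × 2 + 102 × 4 = 648. Completers only: 102 × 6 = 612. The screening sample is not counted.

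**3. Plates.** 720/80 = 9 and 720/40 = 18. Even 612 samples with all 96 wells used for unknowns need 612/96 = 6.4, so 7 plates. One plate is impossible under any such layout.

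**4. Noise if visits sit on different plates.** Variance of change without plate error = 2 × 0.5² × (1 − 0.5) = 0.25. Plate SD = 2.0 × CV. Added variance is 2 × (2.0 × CV)² if both draws of a visit share a plate, and half that if they do not. Power is for 50 per group with both draws on one plate (normal approximation).

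| CV | Added variance | Inflation, draws together | Inflation, draws apart | Power |
|---|---|---|---|---|
| 5% | 0.02 | 0.27/0.25 = 1.08 | 1.04 | 99.8% |
| 10% | 0.08 | 0.33/0.25 = 1.32 | 1.16 | 99.2% |
| 15% | 0.18 | 0.43/0.25 = 1.72 | 1.36 | 96.8% |

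The t distribution gives 99.7%, 99.1% and 96.5%. At CV 10%, 100 completers carry the information of 100/1.32 = 76 (draws together) or 100/1.16 = 86 (draws apart). With correlation 0 the variance of change is 0.50, and power with draws together is 93.4%, 90.7% and 85.8%, against 94.2% without plate error.

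**5. Bias.** A plate shift common to both arms at a visit drops out of the time-by-treatment contrast. A simulation with visits on separate plates, arms mixed at random and 20 participants per plate gave mean bias of about 0 and type I error near 5% at all three CVs.

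The worst case is plates segregated by arm and visit, three per cell (60 participants × 2 draws / 40 = 3). The net change then carries a shared shift with SD √(4 × (2.0 × CV)²/3) = 0.12, 0.23 and 0.35 pg/ml, against a target of 0.5. With SE 0.10 treated as fixed, type I error is 2 × [1 − Φ(1.96 × 0.10/√(0.10² + shift SD²))], about 20%, 44% and 59%. Simulating 50 per arm, so that the spread between plates also widens the estimated SE, gives about 18%, 39% and 51%.

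**The case against.** The strongest reply is that the documents are silent on plating and do not prescribe a bad layout. Holding every sample to the end is exactly what allows a participant's samples to share a plate, and an additive shift then cancels from the change. The document is a research strategy, plate maps usually sit in laboratory procedures, and the plan cites the laboratory's quality control. This stands to the extent that plate error may enter the change; nothing shows that it will. It does not rescue the sentence, which credits the single run with a control it cannot give.

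A reader might infer three stronger things, and the documents do not support them.

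- **That plating in visit order biases the result.** It does not bias the primary contrast while arms are mixed. Both arms run concurrently in the same weeks and place, so storage order would tend to mix them.
- **That the trial is underpowered as a result.** Power stays far above the stated bound at every CV shown. The figure of 76 effective completers is correct for one layout, but by itself it suggests a shortage that does not exist. The plan's SD of 0.5 may also already contain assay error, in which case adding plate variance counts some of it twice.
- **That the two processing times flatly contradict each other.** Six hours can be read as an outer limit and immediate processing as the usual practice. The documents give no evidence that a delay within that limit harms a marker.

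**Conclusion.** The concern holds in a limited form. The statement that one run controls any assay variability is wrong for a plate assay with 720 planned samples, and neither an allocation rule nor a model term covers the gap. The consequence is avoidable noise, 8% to 72% more variance of change with draws together or 4% to 36% with draws apart, plus an unguarded risk of confounding arm with plate. The stated power survives. Serious type I error, about 18% to 51% by simulation at CVs of 5% to 15%, needs plates segregated by arm, which nothing in the plan suggests but nothing excludes.

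The need for more than one plate rests only on the document's sample count and a 96-well format. The inflation and error rates rest on the assumed CVs, correlation and plates per cell. The change is worth making because it is cheap and protects the primary outcome. The processing-time wording is a separate, minor inconsistency.

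**What to change.** Replace the sentence on assay variability with a plate rule:

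- All six IL-6 samples of a participant go on one plate.
- Arms and sites are balanced across plates.
- Samples carry coded labels that hide arm and visit from the laboratory.
- The same rule applies to CRP, sCD14 and d-dimer.

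In the Aim 1 model, add plate as a random effect. If plate error is proportional to level, analyse on the log scale, because a multiplicative shift cancels from a within-person difference only there.

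**Cost.** In duplicate, 40 places hold 6 participants (36 samples), so 120/6 = 20 plates instead of 18. In single wells, 80 places hold 13 participants (78 samples), so 120/13 = 9.2, or 10 plates instead of 9. The four or two places left over on a full plate could hold a common control sample, so that the between-plate CV can be reported. Beyond this the change needs a plate map before the run and one model term, with no extra blood draws.

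Separately, the sponsor should reconcile the two statements on processing time and decide which one holds.
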